PROTOCOL NAME:

Details of sponsor

Ms.[name]

Research Governance

Research and Enterprise Directorate

Queens University Belfast

[name]

[name]

Email: [contact]

Chief Investigator & Research Team Contact Details

Chief Investigator:

[name]

Centre for Public Health

Royal Victoria Hospital

[name]

[name]

[contact]

Email: [contact]

Co-Investigator:

[name]

Belfast Health and Social Care Trust

Royal Victoria Hospital

[name]

[name]

Email: [contact]

Co-Investigator:

[name]

Psychology Department

University of Sussex

[name]

[name]

[contact]

Email: [contact]

Purpose:

To validate a newly developed battery of performance-based tests of visual function to be presented using virtual reality. The tests are intended as potential outcome measures for clinical trials of treatments of eye disease: they measure visual performance in patients with low vision on visual tasks that are relevant for daily life.

Introduction:

The ability of patients to perform vision-related daily living tasks is often a desirable metric for assessing the success of a new therapeutic intervention, particularly for making cost-effectiveness decisions. Next generation virtual reality (VR) technology offers the potential to provide customized and standardized naturalistic environments to test patients safely on performance-based measures of visual function for use in assessing the outcomes of clinical trials. We will develop such performance-based measures of visual function in VR and trial them on patients with low vision who have sight impairment.

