The project team have developed custom performance-based tests of visual function in a VR environment, testing skills including object search, clock face and symbol recognition, recognition of gestures and visually guided action. In the current study we propose to pilot the test battery on healthy able-bodied low-vision patients with bilateral ocular disease. Disease selection will reflect the differing types of visual function loss demonstrated by low vision patients; Central loss (e.g. Stargardt's disease); Peripheral loss (e.g. advanced retinitis pigmentosa), and diffuse loss (e.g. Albinism).

Aims of the Research Project:

1. To validate a new virtual reality (VR)-based battery of performance-based tests of visual function that are relevant for patients' daily lives.
2. To quantify the reproducibility of the performance-based tests.
3. To gather acceptability and ease-of-use data from patients.

Experimental Plan

The test battery.

The test battery, developed by [name] at the University of Sussex, incorporates the following tasks

Object search. Participants identify 30 common household objects (e.g. cups, plates, cutlery) placed in a cluttered simulated living room. An infra-red and optical sensing device (Leap Motion, San Francisco, CA) to detect users' hands and project an image of the hands in real time into the virtual environment. Participants indicate the positions of objects they are instructed to identify by pointing to them in the virtual environment.

Box search. In a variation on the object search task, participants are required to indicate the locations of a series of boxes, one presented on each trial. The boxes have a variety of sizes and colours.

Clock face recognition. Patients view analogue clock hands with circular clock faces. Participants are required to tell the time by a verbal response, which is recorded by the tester. According to the responses, the size of the clock face alters on subsequent trials along a logarithmic scale in an adaptive staircase procedure. The performance measure is the size of clock face at which the participant is able to correctly tell the time.

Gesture recognition. Stimuli are short animations of an avatar performing common gestures including pointing, waving, beckoning, shush and stop⁷. Patients are required to describe the gesture, and performance is recorded by the tester.

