Visually guided action. In this test an avatar rolls a ball towards the patient across a table in the virtual environment. The ball is rolled at random angles and at 5 different speeds. Participants are required to intercept the balls using images of their hands projected into the virtual environment (using the Leap motion developer kit). Performance is measured as the number of accurate interceptions as a function of ball speed.

Pilot Testing with low-vision patients.

[name] and [name] will arrange to pilot our performance-based tests of visual function on 20 patients with low vision aged 20-50, including patients with Stargardt's disease, advanced retinitis pigmentosa and Albinism. All patients will have colour fundus images and OCT scans taken to enable accurate phenotyping. They will each attend the Northern Ireland Clinical Research Facility (NICRF) for 2 x 2-hour sessions. They will be assessed in both sessions on all five performance-based measures, allowing us to monitor the consistency of our measurements across two time-points. We will also gather qualitative data on ease of use and patient comfort. We have chosen to use young patients in this study because they may be more comfortable with using virtual technologies. We hope to explore applications with older patients in future studies.

Study Procedures

Inclusion Criteria:

1. Male and female participants
2. Age 20-50
3. Bilateral sight impairment due to Stargardt's disease, retinitis pigmentosa or albinism.
4. Sight impairment criteria are as follows:
 - Visual acuity of 3 / 60 to 6 / 60 with a full field of vision.
 - Visual acuity of up to 6 / 24 with a moderate reduction of field of vision

Exclusion Criteria:

1. Any physical impairment that would make use of the virtual reality headset difficult or unsafe.
2. A history of vertigo or dizziness.

Clinic Visit 1 and 2:

1. Seeking Consent: The Research Optometrist will take consent. The information leaflet on the study will be given to potential participants at their low vision appointment. After participants have had sufficient time to gauge their involvement we will acquire written informed consent.
2. Demographic Questionnaire (Appendix 1)
3. Habitual Visual Acuity: LogMAR visual acuity will be recorded for each eye with their normal refractive corrections (glasses or contact lenses in place).
4. NEI VFQ 25- interviewer administered version.

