5. Virtual Reality Tests – sufficient time will be given to enable the participant to adjust to the headset and the new tasks.
6. Questionnaire on ease of use and acceptability (Appendix 2)
7. Colour Fundus photographs and Optical Coherence Tomography Retinal Scans.

The total study visit should take approximately 2 hours. Given that the protocol only includes non-invasive visual function tests, the participant should experience minimal pain, discomfort or distress. The tests do require concentration and some participants may find them boring. Some users of VR headsets have reported nausea or dizziness during use so the participant will be warned about this and asked to report if either of these symptoms occur. The test would then be aborted.

Sample Size

This is a small pilot study and therefore we haven't attempted to undertake a formal sample size calculation. However we feel the sample size chosen is sufficient to identify any key issues with using this technology with participants with low vision and also to give some indication of the repeatability of the tests.

Statistical Analysis

Given the pilot nature of this study limited statistical analysis will be undertaken. Greater weight will be given to the responses to the ease of use and acceptability questionnaire. Bland and Altman analysis will be used to investigate the repeatability of the tests.

Visual performance tests in virtual reality using the Oculus rift.

Participants will complete a variety of tasks to assess their visual performance in situations equivalent to those they encounter in daily life. Tests are run via the software Unity and participants are guided through each task by the optometrist.

Study Plan

Activity	Visit 1	Visit 2
Informed consent ¹	X	
Demographics/Medical history	X	
NEI VFQ	X	X
Visual Acuity	X	X
VR test	X	X
Retinal Imaging	X	X
Ease of use questionnaire	X	X

1 Must be dated/signed prior to performing study procedures

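### Bland and Altman analysis is the only repeatability method named, so narrow limits on the bounded tests may reflect scores bunched at floor or ceiling; report spread and floor/ceiling counts beside them

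*Combined protocol and SAP*

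**What the plan says.** The Statistical Analysis section is three sentences long. It opens with "Given the pilot nature of this study limited statistical analysis will be undertaken", puts more weight on the ease-of-use questionnaire, and then covers repeatability with "Bland and Altman analysis will be used to investigate the repeatability of the tests". Neither that section nor any other names a measurement scale for the limits, an ICC, a between-patient SD, a floor or ceiling count, or a width that would be acceptable.

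This sentence serves Aim 2, "To quantify the reproducibility of the performance-based tests". The Purpose section gives the wider use: "The tests are intended as potential outcome measures for clinical trials of treatments of eye disease". The design, under Pilot Testing with low-vision patients, is to run the battery "on 20 patients with low vision aged 20-50". On replication it says "They will be assessed in both sessions on all five performance-based measures".

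Two conventional measures are also taken. Under Clinic Visit 1 and 2, "LogMAR visual acuity will be recorded for each eye", and the next item is the "NEI VFQ 25- interviewer administered version". The Study Plan table marks both at both visits.

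**The concern.** Repeatability of an outcome measure has two parts. One is agreement: how far two readings on the same patient differ. The other is reliability: whether that difference is small compared with the real differences among patients. Limits of agreement address the first part only.

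The gap matters most for bounded scores. If a task is so easy, or so hard, that almost every patient scores at one end, the two visits agree closely because the scores have no room to differ. The limits are then narrow, yet the test says little about anyone's vision. A report giving limits alone would present this as good repeatability. At stake is what Aims 1 and 2 can conclude: a test could be described as repeatable, and so as a promising trial outcome, without evidence that it distinguishes patients.

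**Working it through.** The plan states no SD, limit or acceptance width, so there is no figure to reproduce. The check has three steps.

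**Inputs from the documents**
- 20 patients and two sessions (Pilot Testing with low-vision patients).
- Catch task: 5 ball speeds (The test battery) × 5 trials per speed (Appendix 2, running the tests) = at most 25 interceptions.
- Object and box search: 30 trials each. A trial ends on success or at 30 seconds (Appendix 2). The summary score is not defined, but a count found is bounded at 0 and 30, and a search time is capped at 30 seconds.
- Gestures: correct or incorrect per trial, number of trials not given (Appendix 2).
- Clock task: threshold size from an adaptive staircase on a log scale (The test battery).

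**Step 1: what the limits contain.** Let Sw be the within-patient SD and Sb the between-patient SD.
- Half-width of the 95% limits = 1.96 × √2 × Sw. Sb does not appear.
- ICC = Sb² / (Sb² + Sw²).
- With Sw = 1 the half-width is always 2.77, while the ICC is 0, 0.50, 0.80, 0.90 and 0.97 for Sb = 0, 1, 2, 3 and 6.

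**Step 2: illustration on a 25-trial score.** Success rates are assumed, patients are perfectly stable, and the only error is binomial.
- Everyone at 98%: within-patient variance 25 × 0.98 × 0.02 = 0.49; limits ±1.96 × √(2 × 0.49) = ±1.94; between-patient variance 0; ICC 0.
- Success rates uniform from 0.3 to 0.9: mean of p(1 − p) = 0.6 − (0.36 + 0.03) = 0.21; within-patient variance 25 × 0.21 = 5.25; limits ±1.96 × √10.5 = ±6.35; between-patient variance 625 × 0.03 = 18.75; ICC = 18.75 / 24.0 = 0.78.

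A simulation under a different assumed model (patient ability normal on the logit scale, 400,000 patients per scenario) shows the same pattern:

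| Score | Scenario | Limits | ICC |
|---|---|---|---|
| 30 trials | near ceiling, mean 29.4 | ±2.1 | 0.05 |
| 30 trials | mid-range, wide spread, mean 15.0 | ±6.4 | 0.93 |
| 25 trials | near ceiling, mean 24.5 | ±1.9 | 0.04 |
| 25 trials | mid-range, wide spread, mean 12.5 | ±5.8 | 0.91 |
| 30 trials | mid-range, no spread, mean 15.0 | ±7.6 | 0.00 |

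The last row marks the boundary of the point. Lack of spread alone does not narrow the limits; bunching at an end does. In the extreme case where everyone scores 30 of 30 at both visits, the limits have zero width and the ICC is 0/0, hence undefined. A floor and ceiling count is therefore needed as well as an ICC.

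**Step 3: what 20 patients can deliver.**
- ICC of 0.78 with two visits: F = (1 + 0.78) / (1 − 0.78), or 8.14 before rounding the ICC; the one-way F method gives a 95% CI of 0.53 to 0.91.
- By the same method, an ICC of 0.50 has a CI of 0.09 to 0.77, and 0.90 has 0.77 to 0.96.
- Each limit of agreement is itself uncertain by about ±0.81 SDs of the visit differences (standard error √(1/20 + 1.96²/38) = 0.389 SDs, times t = 2.09).

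**The case against.** The strongest reply is that Bland and Altman analysis is a sound choice. For a treatment trial, error in within-patient change matters, and the limits describe it directly. The standard plot puts the mean on the horizontal axis, so with 20 patients a test at ceiling would show as points stacked at one end. This stands in part: a careful reader may notice, but the plan asks for no such reading and no figure to report.

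The illustration is also an assumed extreme. Recruitment deliberately spans central, peripheral and diffuse loss, the clock staircase adapts to the patient, and catches are scored by ball speed, so a total out of 25 is a simplification. Nothing in the documents shows that any test is at floor or ceiling. All of this stands. It limits how likely the problem is, not whether the planned summary would reveal it. Scored by speed, each catch result is bounded at 5, so splitting the total does not remove the bound.

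The ICC has weaknesses of its own: it depends on case mix, three contrasting diseases could raise it, and it is imprecise here. That is a reason to show both SDs and the CI, not to omit the comparison.

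A reader might go further and infer any of the following, which the documents do not support:
- **That the limits will be absolute, in raw units.** The plan gives no scale. Log or ratio limits are open to it, though they would not bring in between-patient spread.
- **That the five tests will be ranked, or some chosen to take forward, on their limits.** No section describes either. Limits in each test's own unit are a normal result, and the difference in units matters only if tests are ranked.
- **That acuity and the NEI VFQ-25 should serve as the yardstick.** Comparing repeatability with standard measures is not an aim, and patients are selected on acuity. The full-field criterion runs from 3/60 to 6/60, or logMAR 1.30 to 1.00. If uniform on that range, the SD is 0.30/√12 = 0.087. With an assumed within-patient SD of 0.05 to 0.08, the acuity ICC would be about 0.75 to 0.54 through range restriction alone. The field-loss group, admitted up to 6/24, would widen the range somewhat.

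**Conclusion.** The point holds in a limited form. Bland and Altman analysis is the only repeatability method named, its limits carry no information on between-patient spread, and no summary of spread or of floor and ceiling is planned. On the bounded tests, narrow limits are therefore ambiguous: they may mean low error, or scores with no room to vary. The clock staircase is less exposed.

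Under the assumed success rates, the uninformative 25-trial score has limits less than a third as wide as the informative one (1.94 / 6.35 = 0.31), with an ICC of 0 against 0.78. That shows what can happen. It does not predict what this battery will do. It rests on stable patients, binomial error and bunching at an end of the scale.

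The importance is moderate to low. This is a declared pilot, its stated hope is only an indication of repeatability, and both visits' data are kept, so the extra statistics could still be calculated later. Specifying them now improves what Aims 1 and 2 can conclude.

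**What to change.** Keep the Bland and Altman analysis. Add to Statistical Analysis that, for each virtual reality test, the report will also give:
- the within-patient SD and the between-patient SD;
- the ICC with its 95% CI, or a statement that it cannot be estimated because scores do not vary;
- the number of patients at floor and at ceiling at each visit.

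State that no test will be called repeatable on its limits alone. This requires the score for each test to be defined, including the search tasks, so that floor and ceiling have a meaning.

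The same statistics for logMAR acuity and the NEI VFQ-25 may be shown, but descriptively only, with a note that the acuity ICC is affected by selection on acuity.

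The cost is a few sentences and a few lines of code, with no new data, visits or patient burden. The drawback is that the ICC depends on case mix and is imprecise with 20 patients, so it should always appear with both SDs and its CI.

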Appendix 1: Measuring Visual Acuity

1.1 ETDRS LogMAR Visual Acuity Charts

- There are a number of ETDRS charts. For the purposes of the cohort study only Charts 1 and 2 and Chart R are needed.
- Chart R is used for refraction.
- After refraction is complete Charts 1 and 2 are used for testing the right and left eye respectively.
- Each line has 5 uniformly sized and spaced letters which decrease progressively in size from the top most line.

LogMAR charts were developed and popularised by Bailey and Lovie and hence they are sometimes referred to as Bailey Lovie Charts. The visual angle is largest with the largest letters. The advantage of these charts is that there is a geometric progression of the visual angle with a doubling or a halving with every 3 line change. Therefore calculation of the visual angle is very simple and allowances are made for the testing distance.

- The charts may be standardised for testing at 4 M or testing at 3M.
- Regardless, they may be used at any testing distance as long as the appropriate conversions are clearly understood.
- Changing the testing distance simply extends the range of acuity the chart can test.
- Thus for example when used at a distance of 4M the acuity range is - 0.3 logMAR to 1.0.
- By moving the chart to 2M, the range becomes 0.0 logMAR to 1.3.
- When testing is undertaken at 1M, acuities as worse as 1.6 can be assessed.
- Although standardised for the 4 M distance, the chart can be easily used at 2M or 1M .
- In order to obtain an acuity, when the chart has been used at 2M or 1M the examiner simply adds 15 letters or 0 letters (for 2M and 1M respectively) to the number of letters read at the testing distance.

- Full details on how the results of the tests should be scored and recorded will be provided along with the forms used to record acuity.

1.2 **Retroilluminated Visual Acuity Box**

- The illuminated box can be mounted on a wall or be used free standing.
- The box should be placed so that the top of the third row of letters (0.8 logMAR at 4 Metres testing distance) is 49 ± 2 (124.5 \pm 5.1cm) inches from the floor.

1.3 **Ambient lighting**

- Most of the room lights should be turned off during the visual acuity test.
- Retro-illumination within the box itself provides the appropriate level of illumination to undertake the test and should also allow the examiner to record the test results without any additional lighting..

1.4 **Visual Acuity Lanes**

- A distance of 2 meters (78.7 inches) is required between the patient's eyes and the visual acuity chart for the 2 meter test, and a distance of exactly 1 meter (39.37 inches) is required for the 1 meter test.
- Wall-mounted box: In addition to the 4 meter lane, 17.78 cm (7 inches) must be allowed for the depth of the box plus space for the patient. If space is insufficient, the test may be undertaken at any specified distance as long as this is taken into account during the recording of information.
- Stand-mounted box: In addition to the 4 meter lane, 33.02cm (13 inches) must be allowed for the stand's casters plus space for the patient.

1.5 **Marking the distance**

- The distances are measured from the eye of the patient, seated comfortably in a chair with his or her back firmly placed against the

chairs back, to the centre of the second (left eye) or fourth letter (right eye) of the third line of the chart. The horizontal distance must be measured individually for each examination. 1 or 2 meter sticks can be used.

1.6 Recording of VA

- Each eye should be tested separately at a specified distance
- The testing distance should be clearly marked on the record of acuity form
- Use chart 1 to test the RE and chart 2 to test the LE
- Place the appropriate correction in the trial frame on the eye to be tested and ensure that the fellow eye is occluded properly.
- Ask the patient to read steadily line by line.
- The examiner can make reassuring comments but should not tell the patient whether a letter is correctly or incorrectly identified.
- The patient may be encouraged to guess letters and if letters are missed the examiner may point to the row of letters as patients often use eccentric fixation.
- When visual acuity is worse than logMAR 0.8 (that is fewer than 15 letters read at 4M testing distance) testing should be repeated at 1 meter.
- If a patient is unable to read any letters on the largest line at 1 meter vision should be checked with a pinhole to assess whether reduced vision is due, at least in part, to a very large refractive error.
- For the purposes of recording VA, each letter read correctly should be circled.
- Cross out letters incorrectly identified.
- If a patient skips a letter leave this unmarked, though the patient may be encouraged to reattempt the line on which the letters were missed.
- Patients are also encouraged to guess and the examiner should not stop until a minimum of 3 letters on one row are incorrectly identified.

1.7 Scoring.

- VA may recorded as a linear variable ie. simply enter the number of letters read and the testing distance.
- If no letters are read at 4M, only the score at the 1M testing distance is entered.
- If fewer than 20 letters are read at the 4 M testing distance, the number of letters correctly identified at this distance is added to the score obtained on the 1M testing distance.
- If more than 20 letters are read at 4M, the total read at 4 M is increased by a further 30.
- If the 2 M testing distance is used simply add 15 letters instead of 30 to the score
- If a visual angle is required, the line on which a minimum of 3 letters are correctly identified is entered as the visual acuity.
- At each follow-up visit, the refraction recorded at the previous visit may be used as the beginning approximate refraction for each eye

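### Appendix 1's combined letter-score rules disagree for eyes tested at 4 m: 15–19 letters need a 1 m reading that 1.6 does not call for, exactly 20 has no branch, and the 4 m + 1 m sum has no stated line limit

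*Combined protocol and SAP*

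**What the plan says.** The rules are in Appendix 1 of the combined protocol and SAP.

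- **Trigger for a second distance (1.6).** Acuity worse than 0.8 logMAR, which 1.6 equates to "fewer than 15 letters read at 4M testing distance) testing should be repeated at 1 meter".
- **How far the patient reads (1.6).** "the examiner should not stop until a minimum of 3 letters on one row are incorrectly identified". No stop after a fixed number of lines at 1 m is given.
- **Combined score, lower branch (1.7).** "If fewer than 20 letters are read at the 4 M testing distance, the number of letters correctly identified at this distance is added"; the other term of the sum is the 1 m score.
- **Combined score, upper branch (1.7).** "If more than 20 letters are read at 4M, the total read at 4 M is increased by a further 30".
- **Nothing read at 4 m (1.7).** "If no letters are read at 4M, only the score at the 1M testing distance is entered".
- **2 m testing (1.7).** "If the 2 M testing distance is used simply add 15 letters instead of 30 to the score".
- **Conversion (1.1).** A 2 m count is raised by 15 letters and a 1 m count by 0, so the 1 m count stands as the full score.

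Section 1.7 also allows the letters read and the testing distance to be entered as they are, and it has a separate rule for a line-based acuity. Section 1.1 says full scoring details will come with the record forms, which are not part of the document. The Study Plan table has acuity at both visits, and the Clinic Visit section says it is taken for each eye.

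**The concern.** Sections 1.6 and 1.7 sort eyes by the letter count at 4 m but use different cut-points: 15 for testing, 20 for scoring. Eyes between the two fall to a scoring branch whose second term the testing rule does not request. The two scoring branches also leave out their shared boundary value. Where a 1 m reading does exist, 1.7 adds the 4 m letters to it while 1.1 treats it as already complete, so the same readings can give two totals.

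What is at stake is the consistency of the acuity record. Two examiners, or one examiner at two visits, could follow the appendix in good faith and give an unchanged eye different letter scores. That would weaken the description of participants, and any later comparison of virtual reality performance with acuity.

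**Working it through.** **Inputs (Appendix 1, 1.1).** Five letters per line. The visual angle doubles every three lines. The chart covers 1.0 to -0.3 logMAR at 4 m, and its largest line is 1.3 at 2 m and 1.6 at 1 m.

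**Step 1: reproduce the plan's own figures.**
- Per letter: log10(2) / 3 / 5 = 0.02 logMAR.
- 4 m to 2 m: log10(4/2) = 0.301, and 0.301 / 0.02 = 15 letters.
- 4 m to 1 m: log10(4/1) = 0.602, and 0.602 / 0.02 = 30 letters.
- Letters at 4 m: n = (1.1 - logMAR) / 0.02. At 0.8 logMAR, n = 0.3 / 0.02 = 15, which agrees with 1.6.

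The +15, +30 and 0.8 logMAR figures therefore all reproduce.

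**Step 2: find the consistent score.** Assume the eye resolves the same angular size at each distance. For n of 1 or more, it reads n + 15 letters at 2 m and n + 30 at 1 m. Then:
- 4 m rule: n + 30.
- 2 m rule: (n + 15) + 15 = n + 30.
- 1 m rule in 1.1: (n + 30) + 0 = n + 30.

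The three single-distance routes agree, so n + 30 is the appendix's own scale.

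**Step 3: apply 1.6 and 1.7 as written.** With the 1 m count limited to c lines, the 1.7 sum is n + min(n + 30, 5c). With no limit it is n + (n + 30) = 2n + 30.

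| n at 4 m | logMAR | 1 m test called for by 1.6 | Consistent score | 1.7, all 1 m lines | 1.7, first six 1 m lines |
|---|---|---|---|---|---|
| 1 | 1.08 | yes | 31 | 32 | 31 |
| 5 | 1.00 | yes | 35 | 40 | 35 |
| 10 | 0.90 | yes | 40 | 50 | 40 |
| 14 | 0.82 | yes | 44 | 58 | 44 |
| 15 | 0.80 | no | 45 | addend not called for | addend not called for |
| 19 | 0.72 | no | 49 | addend not called for | addend not called for |
| 20 | 0.70 | no | 50 | no branch | no branch |
| 21 | 0.68 | no | 51 | 51 (+30 branch) | 51 (+30 branch) |
| 25 | 0.60 | no | 55 | 55 (+30 branch) | 55 (+30 branch) |

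For n = 1–14 the over-score is n with no limit (14 × 0.02 = 0.28 logMAR at most), min(n, 10) with eight lines, min(n, 5) with seven, and 0 with six. With no limit the scale is also out of order: 2 × 11 + 30 = 52, so eyes reading 11–14 letters (52–58) would outscore a better eye reading 21 (51).

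**Step 4: the case n = 0.** Here the 4 m chart has run out, so n + 30 does not apply. At 1 m, letters = (1.7 - logMAR) / 0.02. An eye at 3/60 (1.30 logMAR) reads 0.40 / 0.02 = 20 letters, and 1.7 enters that count alone. There is no over-score.

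**Step 5: which eligible eyes are affected.** Take the Inclusion Criteria as applying to each eye.
- Full field, 3/60 to 6/60: 1.30 to 1.00 logMAR, so 0 to 5 letters at 4 m. The 15–19 and 20 problems do not arise, and the over-score is at most about 5.
- Reduced field, up to 6/24: log10(24/6) = 0.602 logMAR, about 25 letters at 4 m. All three problems can arise.

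The document does not say how many eyes fall in each group.

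**The case against.** The strongest case against is that little depends on this, and that the text leaves ways around it.

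- **A reader might infer that eyes reading 15–20 letters cannot be scored at all.** The document does not support that. Section 1.7 allows raw letters with distance, and 1.6 requires the distance on the form ("The testing distance should be clearly marked on the record of acuity form") and each correct letter circled. The line rule also remains: "If a visual angle is required, the line on which a minimum of 3 letters are correctly identified is entered as the visual acuity". Only the combined score is undefined.
- **A reader might infer that eyes reading 15–19 letters would be recorded 30 letters too low.** That would require the examiner to drop a term that 1.7 expressly asks for. Section 1.6 does not forbid a 1 m test in these eyes, so an examiner could do one because 1.7 needs it. The two sections would still differ on who is tested at 1 m, and the line-limit question would then extend to these eyes.
- **A reader might take the 14-letter figure as a demonstrated error.** It is the worst case of an ambiguity. It needs every 1 m line to be counted and equal thresholds at each distance. The missing limit and the stopping rule permit that reading, but they do not compel it.
- **The record forms might settle everything.** They are promised with full scoring details and could resolve all three parts, so it cannot be said that examiners will have to improvise. The appendix would still disagree with itself.
- **Consequence.** This objection stands. Statistical analysis is limited, greater weight goes to the acceptability questionnaire, and the Bland and Altman analysis is of the tests, most naturally the virtual reality battery. The letter score is optional and 4 m testing is not mandatory. A reader might infer that the repeatability results are at risk, but no stated analysis uses the letter score.

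**Conclusion.** The point holds as an internal inconsistency of minor severity, confined to the combined letter score of eyes tested at 4 m. The threshold mismatch (15–19 letters) and the gap at exactly 20 follow from the wording alone and need no assumption. The conflict between 1.1 and 1.7 for 1–14 letters is an over-score of 0 to 14 letters. Its size depends on how many 1 m lines are counted and on the equal-threshold assumption. Eyes tested only at 2 m or 1 m, eyes reading nothing at 4 m, and line-based acuities are scored consistently. Where the circled letters and testing distance have been kept, affected scores can be recalculated.

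**What to change.** Use one threshold in 1.6 and 1.7. Fifteen letters already matches 1.6 and adds no testing.

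- **15 or more letters at 4 m, including 20:** score n + 30.
- **1–14 letters at 4 m:** state one method. For example, add the 4 m letters to a 1 m count limited to the first six lines (maximum 30). Under the equal-threshold assumption this gives n + 30 and joins the upper branch without a jump (44 at n = 14, 45 at n = 15). Only one method should be named, because with real readings two methods could differ.
- **0 letters at 4 m:** keep the existing rule of entering the 1 m count alone. It may be below 30 (about 20 for an eye at 3/60).

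Then bring the 1 m conversion in 1.1 and the acuity form into line with this rule. The cost is a few edited bullets and the matching line on the form.
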